9.2 Analysis Datasets

We will have two datasets:

- 1) An Intention-To-Treat (ITT) dataset including all randomized participants (those eligible after screening); and
- 2) A Modified Intention-To-Treat (MITT) dataset including all participants who undergo at least one scan/t-PBM session.

The MITT dataset will be used for almost all analyses. We will use the ITT dataset only to query whether there are any demographic or clinical differences between the groups of subjects that do and do not undergo at least one scan.

9.3 Description of Statistical Methods

9.3.1 General Approach

Before any statistical techniques are applied, the distribution of all variables will be investigated using descriptive statistics and outliers will be examined. Where necessary, non-parametric statistical methods will be used rather than relying on distributional assumptions. Since the main goal of the study is to obtain evidence about the mechanism of action, the feasibility of implementation, and the potential for efficacy of novel treatment strategies that, if warranted, will be tested in future confirmatory studies, the emphasis of the statistical analysis will be on estimation (with effect sizes and confidence intervals) rather than on hypothesis testing. Where formal hypothesis testing is employed, significance will be judged at 5% level, two-sided.

9.3.2 Analysis of the Primary Efficacy Endpoint(s)

For each subject at each t-PBM dose (including sham) we will obtain the BOLD signal change measured in left and right dorsolateral prefrontal cortical regions of interest. These measures will be modeled as a function of dose (considered a categorical variable with 4 levels) using mixed effects models¹¹⁷, including random subject intercepts to account for the potentially correlated measures on the same subject. Since the doses will be presented to subjects in a random order, the initial model will also include order of the dose (a continuous variable) and all interactions between the dose and the order. If there is evidence for an interaction effect between dose and order, this effect will be investigated to understand how the dose effect varies as a function of week of treatment, and in such case effect size of the t-PBM doses will be estimated using only the data when the dose was given in the first week. If there is no interaction between dose and order, the order variable and the interactions will be omitted and the resulting model will be used to estimate the mean BOLD signal measures at each dose and the differences between each active t-PBM dose and sham.

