2.1.4 t-PBM Effects on Cerebral Blood Flow (CBF): In vivo t-PBM has robust and immediate effects on CBF. In rats, t-PBM at 660 nm with a LED device (9 mW/cm²) was associated with increased oxygen consumption in the frontal cortex⁹⁵, while in mice NIR (808 nm) t-PBM with laser (1.6 W/cm²) resulted in 30% increased CBF⁹⁶. In healthy humans, t-PBM with a 3.4W laser (1064 nm) led to increased

concentration of oxygenated hemoglobin²⁰, while in elderly women t-PBM with a 0.2W LED (627 nm) increased blood flow in the middle cerebral and basilar arteries¹⁹. In chronic traumatic brain injury (TBI) patients, t-PBM with a 3.3W LED device (629 and 850nm) increased CBF (measured by SPECT)³⁶. Our own preliminary data (Section 2.4) show immediate increase in CBF [measured as blood-oxygenation-level dependent (BOLD) signal on fMRI] in healthy volunteers exposed to 808 nm laser NIR. Therefore, changes in CBF during t-PBM administration, measured as changes in BOLD fMRI signal, is an excellent target engagement biomarker. Secondarily, t-PBM also has a modulatory effect on cortical excitability, reducing motor evoked potentials elicited by TMS¹⁵ and may result in increased functional connectivity in the default mode network⁹⁷.

2.1.5 t-PBM Cellular Mechanisms: The NIR delivered through t-PBM is absorbed by a mitochondrial enzyme and chromophore, cytochrome c oxidase (CCO), and is only minimally dissipated as thermal energy^{53,54}. The peak absorption of light energy by CCO occurs at four different wavelengths; one of these peaks is 812–846 nm⁵⁵, overlapping with the wavelengths with best brain penetration described above.

Depression is associated with hypometabolism in specific brain areas⁵⁶⁻⁵⁹ and mitochondrial dysfunction⁶⁰⁻⁶⁴. Results in cellular and animal models indicate that PBM can enhance mitochondrial activity. NIR delivers energy to the CCO and stimulates the mitochondrial respiratory chain leading to increased ATP production^{54,65,66}. In addition, NIR can improve mitochondrial activity by promoting the dissociation of nitric oxide (NO) from the CCO releasing the binding site for oxygen and restoring oxidative phosphorylation⁵³. The released NO may also act as a local vasodilator⁶⁷. A study on isolated mitochondria also reported increased RNA and protein synthesis after irradiation with a low-level laser (632.8 nm)⁶⁸.

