Preliminary data on t-PBM effect on Cerebral Blood Flow (measured with fMRI-BOLD): We have collected data from n=20 subjects undergoing tPBM during resting state fMRI¹⁰³. To disambiguate the effects of CBF from those of blood oxygenation, we employed a multi-echo MR sequence¹⁰⁴. Subjects' brain activity in the form of the BOLD signal was acquired continuously for 30 minutes, with tPBM applied for 10 minutes beginning at minute 11. Stimulation was delivered with a laser (808 nm), with an intensity of 318 mW/cm² and a spot size of 1 cm² to the right forehead (standard EEG electrode location "Fp2"). Whole-brain voxel-wise statistical Chow tests¹⁰⁵ were conducted separately at each echo of the group-averaged BOLD in order to detect significant changes during and after t-PBM, relative to the pre-stimulation baseline period.

During t-PBM, we found a significant modulation of early-echo (13 ms) BOLD in a cluster of 214 voxels in the right medial frontal gyrus (MFG), 24 mm from the site of light incidence (Figure 2). A cluster of 154 voxels in the right MFG, 22.4 mm from incidence, was also found at echo 2 (34 ms). Four smaller clusters were detected at echo 3 (56 ms), including one in the right superior frontal gyrus (SFG), 22.5 mm from incidence. Interestingly, we found that t-PBM produced an effect on the early-echo BOLD that outlasted the stimulation. A cluster of 218 significant voxels centered in the MFG was found at a distance of 28.7 mm from incidence. The presence of significant BOLD effects at all echos, including the early-echo which is insensitive to blood oxygenation, suggests that CBF was increased during and after t-PBM.

Impact: *Thus, we are in a position to employ quantitative changes in fMRI-BOLD as a biomarker for target engagement during t-PBM.*

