We will use a pulse wave for the high dose because pulsing can prevent skin warming and discomfort thus facilitating enrollment and retention and safeguarding the integrity of the single blind. Safety data from three previously referenced stroke RCTs including 1,410 participants^{21, 22, 100} offer ample evidence that a 700 mW/cm² continuous wave dose is safe. However, testing during the development of our study-specific device suggests that some participants may experience it as “hot” and/or unpleasant and be able to distinguish it from the sham and lower doses. Offering the pulsed high dose instead allows us to expose participants to a similar peak irradiance while lowering the average irradiance, thus reducing the likelihood of inducing skin warming or discomfort.

Table 1. t-PBM Parameters Across 4 Sessions

Parameters	Dose				
	High	Middle	Low	Sham	
Peak Irradiance (mW/cm ²)	833	300	50	0	
Average Irradiance (mW/cm ²)	275	300	50	0	
Time Irradiation (s)	600	333	1200	0	
Average Fluence (J/cm ²)	165	100	60	0	
Total energy (kJ/ cm ²)	2.0	2.4	1.4	0	
Wave Mode	Pulsed	Continuous	Continuous	N/A	
NIR source	Laser	Laser	Laser	N/A	
Wavelength	808nm	808nm	808nm	N/A	
Area of exposure	24cm ²	24cm ²	24cm ²	N/A	
Anatomical targets	F4, F3	F4, F3	F4, F3	F4, F3	

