3.1 Primary Objective

Our primary objective is to identify the t-PBM irradiance dose (50, 300, or ≥ 700 mW/cm 2) with the largest impact on PFC CBF in MDD.

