3.5 Study Endpoints

3.5.1 Primary Study Endpoints

The primary endpoint will be t-PBM effects on BOLD signal.

The specificity of t-PBM effects on BOLD signal increases will be assessed by testing three irradiance doses covering a wide range (50, 300 and ≥ 700 mW/cm 2) versus sham. If a reliable effect on BOLD (compared to sham, the BOLD increase at the optimal dose will have an effect size of Cohen's $d \geq 0.5$) is seen with PBM, the study validate BOLD fMRI as a robust biomarker of target engagement for t-PBM and act as a "go" signal. In contrast, if none of the t-PBM doses yield reliable BOLD increases, this will fail the putative mechanism (*no go*).

Rationale for the effect size (E.S.) threshold: We have previously observed large effect size changes in BOLD (Cohen's $d=0.6$) after a single administration of t-PBM (at 318 mW/cm 2)¹⁰³. In our clinical pilot study, significant, large effect size improvements in depressive symptoms were reported in MDD after 8 weeks (Cohen's $d=1.5$, $n=21$)³⁵. Given these preliminary results, we will use as threshold for the Go/No-Go decision an effect of t-PBM on BOLD at one dose (but not all doses, vs. sham) of magnitude Cohen's $d > 0.5$ (at least medium size).

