5.1.4 Duration of Therapy

Participants will undergo three sessions of active and one session of sham t-PBM, all during MR scanning. The duration of irradiation is 0, 3.33 or 20 minutes, depending on randomization; however, each session will last a total of 20 minutes to maintain blinding.

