6.2.3 Experimental Phase

Duration: 4 visits over 4-8 weeks

Timing: No more than 2 weeks between each visit.

While the provision of study treatment requires clinic attendance, we may conduct other components of the experimental visits remotely.

At each of the four visits, study staff will:

- *Record vital signs;
- Administer
MADRS,
CGI-I (except Visit 1 as this will be considered a baseline rating),
CGI-S,
C-SSRS, and
- MRI Safety Checklist; Record concomitant medications/therapies;
- *Administer the t-PBM session during MR Scanning;
- Record adverse events as reported by participant or observed by investigator.

In addition, participants will complete:

- PANAS,
- PBQ
- PCQ
- SDQ,
- ASQ,
- SAFTEE

- Neuro-QoL
- Q-LES-Q-SF, and
- TSRQ

MGH Site Neuronavigation: The BrainSight Neuronavigation System will be used at the MGH site to track the initial placement of the laser device on the subject's forehead and will be utilized to ensure accurate replication of positioning at each experimental visit. This is a recording device that does not involve any added risk or stimulation. Traditionally, this device is used to record precise location of EEG electrodes and transcranial magnetic stimulation (TMS) coils. In our case, we will be using it to record the position of the outlet of the laser before every PBM session. The BrainSight Neuronavigation System is FDA approved and is used as indicated. This device bounces light off of trackers that are placed on the forehead. Study staff lightly place a wand at various spots on the head. The system correlates the position of the wand with that of the trackers to precisely record the location of the head in relation to the photobiomodulation stimulation device. This is useful for later analysis, in which we will co-register the recorded laser position to the subject's MRI.

- For the NKI/NYU scans, lipid capsules are affixed to the device for demarcation of device location in the scans.

MR: Scanning will begin with acquisition of structural images and (for most subjects) a baseline MR thermometry scan. Subsequently we will collect approximately 60 minutes of functional data collection including ~20 minutes before t-PBM, ~20 minutes coinciding with t-PBM, and ~20 minutes following t-PBM, as well as (for most subjects) a post-t-PBM MR thermometry scan. (For technical and logistical reasons, we may opt to skip the thermometry scan for some subjects.)

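### Does the undefined BOLD window, with light on for different times at each dose, bias the dose ranking enough to require an equal-exposure primary window?

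*Combined protocol and SAP*

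**What the plan says.** Section 3.1 states the aim: "Our primary objective is to identify the t-PBM irradiance dose" with the largest impact on prefrontal blood flow. Section 9.3.2 describes the measure only as "we will obtain the BOLD signal change measured in left and right dorsolateral prefrontal cortical regions of interest", and section 3.5.1 adds no window. Section 6.2.3 divides functional scanning into about "20 minutes before t-PBM, ~20 minutes coinciding with t-PBM, and ~20 minutes following t-PBM". Section 5.1.4 says "each session will last a total of 20 minutes to maintain blinding", while Table 1 in section 2.4 gives irradiation times of 600 s (High), 333 s (Middle) and 1200 s (Low).

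The text points to more than one window. Section 2.1.4 calls the biomarker "changes in CBF during t-PBM administration, measured as changes in BOLD fMRI signal". Section 3.5.1 says the pilot effect of 0.6 behind the Go/No-Go threshold was seen "after a single administration of t-PBM". In the pilot the scan ran for 30 minutes "with tPBM applied for 10 minutes beginning at minute 11" (section 2.3), and the effect of 1.54 compared the signal just before onset with the signal 200 s after onset (section 2.5).

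**The concern.** With no window named, an analyst might fall back on the three 20-minute blocks and take the during-block mean minus the pre-block mean. Part of that block is dark, and the dark part differs by dose. If the effect fades within minutes of light-off, the block mean mixes irradiance with exposure time. Middle, the dose closest to the pilot's 318 mW/cm², would be diluted most and Low not at all.

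At stake are the choice of dose, which is the primary objective, and the Go/No-Go decision at d of 0.5. A real Middle effect could fall below the threshold, or a longer exposure could be carried forward as if it were a better irradiance. The remedy that suggests itself is to make the first 333 s after laser onset, when all three active doses are lit, the primary window.

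**Working it through.** **Precision in section 9.4.** 30 × 0.80 = 24 per dose. The standard error of a contrast in SD units, treating doses as independent groups, is √(2/24) = 0.289. Half-widths are 1.28 × 0.289 = 0.37 (80%) and 1.96 × 0.289 = 0.57 (95%), as stated. The choice of window does not alter these figures in SD units.

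**Light-off time in the during block (Table 1).** Middle 1200 − 333 = 867 s; High 1200 − 600 = 600 s; Low 0 s. Lit share: 28%, 50%, 100%.

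**Dilution of a block mean.** Assume that light starts with the block, that the effect is constant while lit, and that it then decays with time constant τ = half-life/ln 2. The block mean is the lit effect times [on + τ(1 − exp(−off/τ))]/1200. The documents give no half-life, so a range is shown. The last column applies the Middle factor to a lit effect of 0.6.

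| Half-life | Middle | High | Low | Low/Middle | High/Middle | Middle d |
|---|---|---|---|---|---|---|
| 0 | 0.278 | 0.500 | 1 | 3.6 | 1.8 | 0.17 |
| 2 min | 0.421 | 0.640 | 1 | 2.4 | 1.5 | 0.25 |
| 5 min | 0.590 | 0.771 | 1 | 1.7 | 1.3 | 0.35 |
| 10 min | 0.734 | 0.861 | 1 | 1.4 | 1.2 | 0.44 |
| Full persistence | 1 | 1 | 1 | 1.0 | 1.0 | 0.60 |

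Under this model the diluted Middle d reaches 0.5 at a half-life of about 18 minutes. That assumes equal SDs in both windows. If all the noise averaged down with window length, the block d would be divided by √(333/1200) = 0.527. It would then be 0.17/0.527 = 0.32 at half-life 0 but 0.35/0.527 = 0.67 at 5 minutes, above the 0.60 seen while lit. The sign of the effect on the Go decision is therefore not settled.

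**After block.** Every dose is off for the whole block, so light-off time does not differ. Only the delay since light-off can differ (867, 600, 0 s), and only if irradiation starts with the session, which no section states.

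**Is Low favoured?** Three other response models, for the during block (Middle/High/Low):
- Accumulated fluence without decay, averaged over 1200 s. Middle (½ × 100 × 333 + 100 × 867)/1200 = 86; High (½ × 165 × 600 + 165 × 600)/1200 = 124; Low ½ × 60 = 30 J/cm².
- Peak irradiance, no persistence: 300 × 0.278 = 83; 833 × 0.5 = 416; 50.
- Average irradiance, no persistence: 83; 275 × 0.5 = 137; 50.

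Low is last in all three. It gains on Middle only if its effect while lit is more than 1/3.6 of Middle's with no persistence, although its irradiance is one sixth (50 against 300).

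**What a 333 s window does.** Fluence delivered by 333 s is 300 × 0.333 = 99.9, 275 × 0.333 = 91.6 and 50 × 0.333 = 16.7 J/cm². Against full-session values of 100, 165 and 60, that is 100%, 56% and 28%. Mean accumulated fluence over the window is half of each: 50, 46 and 8. Under the fluence model the lead passes from High (124 v 86 in the block) to Middle (50 v 46). The later second peak that section 2.5 describes within the pilot's 10-minute stimulation may also fall outside 333 s.

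**The case for a change.** The strongest case for a change is that the imbalance in Table 1 is certain and that the window can decide the winner. With assumed lit effects of 0.60, 0.45 and 0.30 (Middle, High, Low), 24 per dose and half the variance between subjects, simulation ranks Middle first in 74% of trials over 0–333 s. In the during block the figure is 17%, 26%, 39% and 52% at half-lives of 0, 2, 5 and 10 minutes. With independent groups it is 64% against 21%, 28%, 38% and 47%. An unstated window also leaves room to choose late. If the best of three windows (correlation 0.9 to 0.3) were taken after seeing results, the null chance that some dose reaches 0.5 would rise from 2% to 3–5%, or from 10% to 15–25% with independent groups. A sentence naming the window costs little.

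The arithmetic stands, and so does the observation that the window is unstated. The inference to a biased plan does not. The ranking figures need Middle to be truly best, a constant response while lit and rapid fading. Section 2.5 describes a response with two peaks, and section 2.3 reports an early-echo effect that outlasted stimulation, so zero persistence is the case least consistent with the pilot. The late-choice figures describe conduct that no section proposes. The dilution arises only if the analyst averages lit and dark time together, which section 9.3.2 does not ask for.

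**Conclusion.** No change to the plan follows. Sections 3.5.1 and 9.3.2 leave out a detail that the imaging analysis has to supply, and sensible choices are already in the documents. The period of administration in section 2.1.4 can be read as the time the light is on. The 200 s reading in section 2.5, which section 9.4 cites for its effect size, precedes light-off at every active dose in Table 1. Neither has the handicap.

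Making 0–333 s primary is a trade-off rather than a correction. Section 2.4 says that changing irradiance also changes exposure time, fluence and total energy, so the doses compared are whole regimens and exposure time is part of each. Equal time from onset is a defensible question, but it leaves fluence unequal, can reverse High and Middle, and still does not isolate irradiance: High is pulsed, with an average irradiance of 275 against Middle's 300 mW/cm².

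The size of the effect in a whole-block mean runs from nil (full persistence) to a factor of 3.6 for Middle against Low (none), conditional on light starting with the block, a constant effect while lit and a half-life that the documents do not give.

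One inconsistency is separate from this conclusion. Table 1 lists 333, 600 and 1200 s, while section 5.1.4 lists 0, 3.33 or 20 minutes; 3.33 minutes is 200 s, and 600 s is absent. The two passages must be reconciled. Taking 200 s for Middle would raise the no-persistence factor to 1200/200 = 6.0 but would not alter the reasoning.

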2.5 Rationale

Why test t-PBM parameters with BOLD fMRI

A novel or innovative therapy would not be clinically justified unless it adds significant value in terms of risk/benefit. The limitations of current treatments in MDD are well-documented [Section 2.1.1]. Preliminary data suggests t-PBM targeting the PFC could be a novel treatment strategy in MDD [Section 2.2.1 and

2.2.2]. However, the t-PBM parameters that would maximize its neural impact and therefore its antidepressant potential are not known. Therefore, this study will apply a novel measurement of changes in BOLD fMRI signal as a marker of changes in CBF in the search for optimal t-PBM parameters, with the **long-term goal of transforming clinical practice for patients with MDD**. Proof of engagement of CBF on PFC would support future clinical testing of this low-cost, time-efficient, accessible and user-friendly intervention in MDD subjects.

We considered alternative measures of CBF, including near-infrared spectroscopy (which is associated with much poorer spatial resolution and can only evaluate CBF changes in the superficial cortex in adults), or PET/SPECT (where changes in CBF over a short period of time would be difficult to quantify, and repeated weekly administrations would be limited by the total dose of radiation). We believe the method we propose offers the best balance of accuracy, spatial resolution and repeatability. In our preliminary data, we found a strong effect at echo 1 (Cohen's $d = 1.54$, when comparing the echo 1 BOLD immediately before light onset with the BOLD 200 seconds after onset, (Fig.3).

[figure not shown]

Fig. 3: Time series of BOLD changes after t-PBM was applied to the right forehead 10 min. into a 30-min. BOLD scan¹⁰³. The duration of stimulation was 10 min. (grey area). The colored time series indicate the subject-averaged BOLD (shown here in a ROI corresponding to the right medial frontal gyrus, MFG) at echos 1 (blue, 13 ms), 2 (red, 34 ms), and 3 (orange, 55 ms). A rapid increase in the BOLD was observed shortly after stimulation onset, while a second peak emerged later in the 10 min. stimulation window.

The project is innovative because (1) it tests t-PBM with near-infrared light, an innovative technology with a well-established safety profile, and (2) it uses changes in CBF, as measured with changes in BOLD fMRI signal, as a state-of-the-art target engagement biomarker.

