9.3.5 Exploratory Analyses

We will quantify 1) depression severity using the MADRS and SDQ scores, 2) anxiety severity using the ASQ scores, and 3) perceived quality of cognition using the Neuro-QoL scores and perceived quality of life using the Q-LES_Q-SF, as assessed at the visit after each dose of t-PBM.

We will model these measures as a function of dose (considered a categorical variable with 4 levels) using mixed effects models¹¹⁷, controlling for baseline scores (from the first scan/t-PBM visit) and including random subject intercepts to account for the potentially correlated measures on the same subject. Since the doses will be presented to subjects in a random order, the initial models will also include order of the dose (a continuous variable) and all interactions between the dose and the order. If there is evidence for an interaction effect between dose and order, this effect will be investigated to understand how the dose effect varies as a function of week of treatment, and in such case effect size of the t-PBM doses will be estimated using only the data when the dose was given in the first week. Whenever we find there is no interaction between dose and order, the order variable and the interactions will be omitted. The resulting models will be used to estimate the mean of each measure at each dose and the differences between each active t-PBM dose and sham.

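### The primary model analyses the within-session BOLD change without the session's own pre-light level as a covariate, so some removable session-to-session noise may remain; this concerns precision, not bias

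*Combined protocol and SAP*

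**What the plan says.** Section 9.3.2 defines the primary outcome in one sentence: "we will obtain the BOLD signal change measured in left and right dorsolateral prefrontal cortical regions of interest". The model has dose as a four-level factor, "including random subject intercepts to account for the potentially correlated measures on the same subject". In addition, "the initial model will also include order of the dose (a continuous variable) and all interactions between the dose and the order"; the order terms are dropped if no interaction is found. Neither this section nor the Protocol Summary includes a term for the session's pre-light signal. The window, echo and scaling of the change (raw or percent) are not defined.

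Section 6.2.3 describes the scan at each of the four visits as "approximately 60 minutes of functional data collection including ~20 minutes before t-PBM, ~20 minutes coinciding with t-PBM, and ~20 minutes following t-PBM". A pre-light measurement of the outcome will therefore exist for every session.

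Section 9.4 expects about 24 observations per dose and a half-width for the optimal-dose effect size of 0.37 (80% CI) or 0.57 (95% CI). It calls this a worst case and expects the mixed model to do somewhat better. Section 3.5.1 bases the Go/No-Go decision on Cohen's d against sham, with a threshold of 0.5. Sections 9.1 and 9.3.1 put estimation with confidence intervals ahead of testing.

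**The concern.** A change score is a regression on baseline with the coefficient fixed at 1. If the pre-light and during-light signals correlate imperfectly across one person's sessions, a session that starts high by chance will tend to show a smaller rise. That scatter enters each dose-sham difference. The random subject intercept removes stable differences between people, but not differences between one person's own sessions, which section 6.2.3 allows to be up to two weeks apart.

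What is at stake is the width of the interval around each dose-sham effect. With about 24 people per dose, and no replacement of dropouts (section 9.5.1), precision has to come from the analysis. The measurement that could supply it is already being collected.

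**Working it through.** **Inputs.** From the plan: 30 participants, 20% dropout, half-widths 0.37 and 0.57 (section 9.4), threshold 0.5 (section 3.5.1). Assumed: rho, the within-person correlation across sessions between pre-light and during-light BOLD, and equal variances for the two. The documents give no rho, so a range is shown.

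**Step 1: reproduce the plan's precision.** n = 30 × 0.80 = 24 per dose. Treating dose and sham as two independent groups with SD 1, SE = sqrt(2/24) = 0.289.
- 80%: 1.2816 × 0.289 = 0.370
- 95%: 1.9600 × 0.289 = 0.566

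Both stated figures reproduce. A paired form, with the SD of the difference as the unit, gives 0.262 and 0.400 and does not match.

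**Step 2: effect of the covariate.** With session-level variance s² before and during the light:
- change score: variance 2s²(1 − rho)
- adjusted for the pre-light level: variance s²(1 − rho²)
- ratio: (1 + rho)/2, so the SE is multiplied by sqrt((1 + rho)/2)

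| rho | SE multiplier | 80% half-width | 95% half-width | Equivalent n per dose |
|---|---|---|---|---|
| unadjusted | 1 | 0.370 | 0.566 | 24 |
| 0.3 | 0.806 | 0.298 | 0.456 | 36.9 |
| 0.5 | 0.866 | 0.320 | 0.490 | 32.0 |
| 0.7 | 0.922 | 0.341 | 0.522 | 28.2 |
| 0.9 | 0.975 | 0.361 | 0.551 | 25.3 |

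Half-widths are in units of the unadjusted change-score SD. Equivalent n is 24 divided by (1 + rho)/2.

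**Step 3: check by simulation.** A four-session crossover with 24 people and subject effects removed (4,000 runs per value) gave SE multipliers of 0.83, 0.87, 0.92 and 0.99 at rho 0.3, 0.5, 0.7 and 0.9. A random-intercept model with the covariate split into participant mean and session deviation (150 runs per value, so rougher) gave 0.86, 0.86, 0.97 and 0.98. The formula is adequate, and slightly optimistic at some values.

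**Step 4: effect on the Go rule.** For a single dose, P(estimated d > 0.5) = Phi((d − 0.5)/SE), with SE 0.289 unadjusted and 0.289 × 0.866 = 0.250 adjusted at rho 0.5.

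| True d | Unadjusted | Adjusted, rho 0.5 |
|---|---|---|
| 0 | 4.2% | 2.3% |
| 0.5 | 50% | 50% |
| 0.6 | 63.5% | 65.5% |

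The largest shift at any true d is about 3.5 percentage points (near d = 0.77, from 82.4% to 85.8%). At rho 0.9 it is under 1 point.

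**The case against.** The strongest reply is that the pre-light level is already used. Section 9.3.2 analyses a change, and section 2.5 describes the preliminary contrast as "when comparing the echo 1 BOLD immediately before light onset with the BOLD 200 seconds after onset", so on the natural reading each session is referenced to its own start. This stands. A reader might infer that chance differences in starting level pass straight into the dose effect. They do not, because subtraction removes the level and only a regression-to-the-mean residue can remain.

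Three further inferences are tempting, and the documents do not support them.

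- **Bias.** Dose order is randomised (section 9.5.1). The change score and the adjusted analysis are both valid, and differ in precision.
- **Inconsistency with section 9.3.5.** Those models are described as "controlling for baseline scores (from the first scan/t-PBM visit". They analyse clinical scale scores rather than changes, and the baseline is one first-visit value per person. The closer parallel is the brain-temperature change in section 9.3.3, which also has no baseline term. The plan treats its two imaging change measures alike.
- **A large effect on the decision.** At rho 0.5, the chance that the 95% interval excludes zero would rise from 41% to 52% at d = 0.5. But the Go rule compares d with 0.5, not with zero, and there the shift is small.

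It is also fair to say that rho may be high. The blocks are adjacent, in the same session and with the same cap placement, so session-wide shifts affect both. If the change is scaled to each session's own baseline, the covariate may add almost nothing. Both points limit the size of the gain. Neither shows that the matter is already handled, because the plan does not define the scaling.

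**Conclusion.** The point holds as a minor, low-cost improvement in precision. The primary model omits a session-level covariate that will be available for every scan, and the random subject intercept does not replace it. Apart from one or two degrees of freedom, the adjusted analysis is at least as precise as the plain change score.

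The size is uncertain. The 95% half-width would fall from 0.57 to between about 0.46 (rho 0.3) and 0.55 (rho 0.9), given equal pre- and during-light variances. Little or nothing is gained if sessions are already rescaled to a common baseline. Because section 9.4 calls 0.57 a worst case, these figures show relative gain and are not forecasts of the planned model's interval. The benefit is mainly a narrower interval, which suits the plan's emphasis on estimation; the Go/No-Go decision itself is hardly affected.

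**What to change.** In section 9.3.2:

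1. State how the BOLD change is computed: windows, echo, and raw or percent scaling. If each session is rescaled to a common baseline, saying so largely answers the point.
2. Otherwise, add the session's mean pre-light BOLD in the same ROI as a prespecified covariate, split into the participant's mean and the session's deviation from it. Compute it from pre-light data only and before any whole-run normalisation, because a run-wide mean would carry part of the light effect into the covariate.
3. Report the dose-sham differences from that model. Standardise Cohen's d by the unadjusted change-score SD. Dividing by the smaller residual SD would raise d against the 0.5 threshold without any larger effect.

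The cost is SAP wording and one or two degrees of freedom. No new data or procedures are needed. Prespecification also rules out a later choice between adjusted and unadjusted estimates near the threshold.
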